8.2 Background Characteristics

8.2.1 Subject Disposition

For the Periods 1 and 2 in Part D, the Period 1 and Washout Period in Part E, and the Period 1 in Part F subject disposition will be summarized as described below.

The number of subjects in the following categories will be summarized by treatment group and overall, for Parts D and F:

- All Subjects Set (randomized or dosed)
- Randomized
- Safety Set
- Randomized but not dosed in the Period 1
- Full Analysis Set (FAS)

The number of subjects in the following categories will be summarized by treatment group and overall for Part E:

- All Subjects Set (randomized or dosed)
- Randomized or dosed in the Period 1
- Randomized
- Safety Set for the Treatment Period
- Randomized but not dosed in the Period 1
- Full Analysis Set (FAS)

The number and percentage (based on FAS) of subjects in each of the following disposition categories will be summarized by treatment group and overall:

- Completed study drug treatment (Separated by Periods 1 and 2 for Part D, and by Period 1 and washout period for Part E)
- Prematurely discontinued treatment and the reason for discontinuation (i.e., discontinued all study drugs) (Separated by Periods 1 and 2 for Part D, and by Period 1 and washout period for Part E)
- Completed study (i.e., completed Safety Follow-up Visit or completed all study drugs and re-entered Study 661-110 without Safety Follow-up per protocol)
- Prematurely discontinued the study and the reason for discontinuation

For the Run-in Period in Part E, a separate disposition table will be provided with the following categories:

- Safety Set for the Run-in Period
- Enrolled but not dosed in the Run-in Period
- Completed treatment in the Run-in Period (i.e., completed randomization)

- Prematurely discontinued treatment during the Run-in Period and the reason for treatment discontinuation (i.e., discontinued all study drugs in the Run-in Period)
- Prematurely discontinued the study during the Run-in Period and the reason for study discontinuation

A listing will be provided by part, for subjects who discontinued treatment (including the Run-in Period in Part E) or who discontinued study with reasons for discontinuation. A randomization listing of subjects will also be provided, by part.

8.2.2 Demographics and Baseline Characteristics

Demographics, medical history and baseline characteristics will be summarized based on the FAS, and presented by treatment group and overall, for each part.

Demographic data will include the following:

- Age at baseline (in years)
- Sex (female and male)
- Ethnicity (Hispanic or Latino, not Hispanic or Latino, and not collected per local regulations)
- Race (White, Black or African American, Asian, American Indian or Alaska Native, Native Hawaiian or Other Pacific Islander, and Other)

Baseline characteristics will include the following:

- Weight (kg)
- Height (cm)
- BMI (kg/m²)

Stratification categories will include the following:

- ppFEV₁ at stratification (< 70 and ≥ 70)

For Part D1, no stratification will be performed.

For Part D2, ppFEV₁ stratification (<70 versus ≥70) will be performed using the screening (Days -28 to -1) ppFEV₁ value.

For Part E, ppFEV₁ stratification (<70 versus ≥70) will be performed using a value obtained at the following visit:

- Screening Visit (Days -56 to -29) for subjects transitioning directly from at least 14 days of uninterrupted TEZ/IVA treatment
- Day -14 Visit (+ 13 days) for all other subjects

For Part F, ppFEV₁ stratification (<70 versus ≥70) will be performed using the screening (Days -28 to -1) ppFEV₁ value.

Disease characteristics will include the following:

- ppFEV₁ at baseline (<40, ≥ 40 to <70, ≥70 to ≤90, >90)

- ppFEV₁ at baseline (continuous)
- Sweat Chloride at baseline (continuous)
- FEV₁ (L) at baseline (continuous)
- CFQ-R Respiratory Symptoms domain at baseline (continuous)
- Prior use of dornase alfa before first dose of study drug in the Treatment Period (Yes, No)
- Prior use of inhaled antibiotic before first dose of study drug in the Treatment Period (Yes, No)
- Prior use of any bronchodilator before first dose of study drug in the Treatment Period (Yes, No)
 - Prior use of any inhaled bronchodilator before first dose of study drug in the Treatment Period (Yes, No)
 - Prior use of any inhaled hypertonic saline before first dose of study drug in the Treatment Period (Yes, No)
 - Prior use of any inhaled corticosteroids before first dose of study drug in the Treatment Period (Yes, No)
 - Infection with *Pseudomonas aeruginosa* at baseline (Positive, Negative)

A summary of medical history will be provided by MedDRA System Organ Class (SOC) and Preferred Term (PT) for the FAS. In addition, the number of subjects reported to have had positive cultures for respiratory pathogens in 2 years prior to screening will be summarized for the FAS. Further, the CFTR genotype for each subject will be provided in an individual subject data listing.

8.2.3 Prior and Concomitant Medications

Medications will be coded using the World Health Organization Drug Dictionary Enhanced (WHO-DDE) and categorized as follows:

For Parts D and F:

Prior medication: any medication that started before the first dose date of study drug, regardless of when the medication ended.

Concomitant medication: medication continued or newly received on or after the first dose date of study drug through the end of the TE period.

Post-treatment medication: medication continued or newly received after the TE period.

For Part E:

Prior medication: any medication that started before the first dose date of study drug in the Run-in Period, regardless of when the medication ended.

Concomitant medication during the Run-in Period: medication continued or newly received on or after the first dose date of study drug during the Run-in Period through the end of the TE period for the Run-in Period.

Concomitant medication during the Treatment Period: medication continued or newly received on or after the first dose date of study drug during the Treatment Period through the end of the TE period for the Treatment Period.

Post-treatment medication: medication continued or newly received after the TE period.

A given medication may be classified as follows: prior, concomitant, post-treatment, both prior and concomitant, both concomitant and post-treatment, or prior, concomitant, and post-treatment. In Part E, concomitant may be concomitant during the Run-in Period, or concomitant during the Treatment Period, or both.

If a medication has a completely missing or partially missing start/stop date and it cannot be determined whether it was taken before the first dose date of study drug, concomitantly, or after the TE period, it will be classified as prior, concomitant, and post-treatment.

Prior medications and concomitant medications will be summarized descriptively using frequency tables by preferred name.

Summaries of medications will be based on the FAS, and presented by treatment group and overall for each part.

Post-treatment medications will be listed by subject.

Details for imputing missing or partial start and/or stop dates of medication are described in [Appendix C](#).

8.2.4 Study Drug Exposure

Study drug exposure (in days) will be calculated as: last dose date of study drug – first dose date of study drug + 1 day, regardless of study drug interruption, and will be summarized descriptively. Study drug exposure will be summarized for the overall study drug period, which includes the Run-in Period, Period 1 of the Treatment Period and Washout Period for Part E, the Period 1 and Period 2 of the Treatment Period for Part D, and include the Period 1 for Part F. Further, study drug exposure for the combined Period 1 of the Treatment Period and Washout Period in Part E will also be summarized descriptively.

Study drug exposure (in weeks) will be summarized descriptively by the number of subjects (n), mean, SD, SE, median, min, and max. It will also be summarized in categories: ≤ 2 weeks, $>2 - \leq 4$ weeks, and > 4 weeks (for Part D); and ≤ 2 weeks, $>2 - \leq 4$ weeks, $>4 - \leq 8$ weeks, >8 weeks (Treatment and washout periods for Part E); ≤ 2 weeks, $>2 - \leq 4$ weeks (for Part F), using counts and percentages. Additionally, the total study drug exposure, defined as the sum total of the study drug exposure across all subjects (in patient-weeks), will be provided.

Exposure summaries will be based on the Safety Set, and presented by treatment group and overall, for each part. For Part E, exposure summaries will be based on the Safety Set for the Treatment Period.

8.2.5 Study Drug Compliance

Percentage of tablets taken will be calculated as: $100 \times [(total\ number\ of\ tablets\ dispensed) - (total\ number\ of\ tablets\ returned)] / (total\ number\ of\ tablets\ planned\ to\ be\ taken\ per\ day \times duration\ of\ study\ drug\ exposure\ in\ days)$. The maximum percentage of tablets taken will be 100%.

Study drug compliance will be calculated as: $100 \times [1 - (\text{total number of days of study drug interruption}) / (\text{duration of study drug exposure in days})]$. A study drug interruption on a given day will be determined by an interruption of all drugs on that day.

Percentage of tablets taken and study drug compliance will be summarized descriptively by the number of subjects (n), mean, SD, SE, median, min, and max. It will also be summarized in categories: <80% and $\geq 80\%$ using frequency tables.

For all parts, study drug compliance and percentage of tablets taken will be summarized for Period 1 only.

Percentage of tablets taken and study drug compliance summaries will be based on the FAS, and presented by treatment group and overall, for each part.

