8.2.6 Important Protocol Deviations

An important protocol deviation (IPD) is a deviation that may significantly affect the completeness, accuracy, or reliability of the study data or that may significantly affect a subject's rights, safety, or well-being. IPD rules will be developed and finalized before database lock. The protocol deviations that should be considered as potential IPDs include, but are not limited to:

- Subject was enrolled in the study despite the violation of inclusion/exclusion criteria
- Subject was less than 80% compliant with study drug
- Subject received prohibited concomitant medications
- Subject received the wrong treatment or incorrect doses
- Subject remained in the study despite meeting withdrawal criteria

Occurrence of any of these events should be considered as potential IPDs, but a blinded team should categorize them as IPDs only if they have the potential to significantly affect the completeness, accuracy, or reliability of the study data or that may significantly affect a subject's rights, safety, or well-being.

IPDs will be provided in an individual subject data listing for each part. Details of the IPD rules are provided in [Appendix D](#).

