8.4.1 Adverse Events

For analysis purposes, AEs will be classified as pretreatment AEs, TEAEs, or post-treatment AEs, defined as follows:

For Parts D and F:

Pretreatment AE: any AE that started before the first dose date of study drug

TEAE: any AE that worsened (either in severity or seriousness) or that was newly developed at or after the first dose date of study drug through the end of the TE period

Post-treatment AE: any AE that worsened (either in severity or seriousness) or that was newly developed beyond the TE period

For Part E:

Pretreatment AE: any AE that started before the first dose date of study drug

TEAE during the Run-in Period: any AE that worsened (either in severity or seriousness) or that was newly developed at or after the first dose date of study drug through the end of the TE period for the Run-in Period

TEAE during the Treatment Period: any AE that worsened (either in severity or seriousness) or that was newly developed at or after the first dose date of study drug through the end of the TE period for the Treatment Period

Post-treatment AE: any AE that worsened (either in severity or seriousness) or that was newly developed beyond the TE period

For AEs with completely missing or partially missing start dates, if there is no clear evidence that the AEs started before or after study treatment, the AEs will be classified as TEAEs.

Details for imputing missing or partial start dates of adverse events are described in [Appendix G](#).

AE summary tables will be presented for TEAEs only, for the TE period for Parts D and F, or the TE period for Treatment Period in Part E, by treatment group and overall, for each part respectively, as applicable, for the following:

- Number of TEAEs (total number of TEAEs only)
- Subjects with any TEAEs
- Subjects with TEAEs by Strongest Relationship
- Subjects with TEAEs by Maximum Severity
- Subjects with TEAEs Leading to Study Drug Discontinuation (Discontinuation of all study drug)

- Subjects with TEAEs Leading to Study Drug Interruption (Interruption of all study drug)
- Subjects with Serious TEAEs
- Subjects with TEAE Leading to Death

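### Interruption, AE-discontinuation and disposition counts register only when every study drug stops, so a lapse in VX-445 alone is missed there and diluted in the tablet count

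*SAP*

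**What the plan says.** SAP 8.2.5 defines two adherence measures for Parts D, E and F.

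- **Study drug compliance** is 100 × (1 − interruption days ÷ exposure days). The rule for an interruption day is: "A study drug interruption on a given day will be determined by an interruption of all drugs on that day".
- **Percentage of tablets taken** is tablets dispensed minus tablets returned, divided by tablets planned. It pools all tablets, has no all-drug condition, and is capped at 100%.

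Both are split at 80%, and on timing the section says: "For all parts, study drug compliance and percentage of tablets taken will be summarized for Period 1 only".

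SAP 8.4.1 qualifies its table of AEs leading to discontinuation with "Discontinuation of all study drug", and the interruption table carries the matching qualifier. SAP 8.2.1 likewise equates premature treatment discontinuation with stopping every study drug.

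Among potential important protocol deviations (IPDs), SAP 8.2.6 lists: "Subject was less than 80% compliant with study drug". Appendix D repeats the 80% limit. Neither place says which measure applies.

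The protocol calls both measures dosing compliance (12.3.2.4) and plans a table of AEs leading to treatment discontinuation (12.3.5.1.2). Neither section has an all-drug condition. SAP 2.1 declares two modifications to the protocol, the treatment-emergent period and a ppFEV₁ sensitivity analysis, and this is not one of them.

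**The concern.** The components are separate tablets. VX-445 has its own tablets, TEZ/IVA is a fixed-dose tablet and the evening IVA dose is a third product (protocol 10.3), so a subject can omit one and take the rest. In Part E both arms take TEZ/IVA throughout, and VX-445 or its placebo is all that differs between them.

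Under the all-drug condition, a subject who stops or skips only VX-445 has no interruption days. That subject does not appear under AEs leading to interruption or discontinuation, nor under premature discontinuation. The exposure summary (SAP 8.2.4) does not help: it runs from first to last dose of study drug, and protocol section 10 defines study drug to include every component.

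Safety and tolerability of VX-445 in combination is a primary objective. The tables that describe how well it was tolerated and taken should show a lapse in VX-445 itself.

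**Working it through.** The plan gives no figure to reproduce, so the check applies the two SAP 8.2.5 formulas to a subject who skips VX-445 on k of D days in Period 1 and takes everything else.

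**Inputs**

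- D = 28 days (4-week Period 1).
- Other tablets in Parts D and E: o = 2 a day (one TEZ/IVA in the morning, one IVA in the evening).
- Other tablets in Part F: o = 5 a day (TEZ 100 mg as two 50-mg tablets, VX-561 150 mg as three 50-mg tablets).
- VX-445 tablets a day, v: not stated. The largest tablet is 100 mg, so a 200-mg dose needs at least two. All groups in a part take the same number (protocol 9.6.2), and Part D2 includes 50, 100 and 200 mg, so placebo tablets could raise the number. I take v = 2 to 4 as an assumption.

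**Formulas**

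- Study drug compliance (SAP rule): 100 × (1 − 0/D) = 100% for every k, because no day has all drugs interrupted.
- Compliance if any drug counts: 100 × (1 − k/D).
- Percentage of tablets taken: 100 × [1 − k·v / ((v + o)·D)].

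**Example, k = 10**

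VX-445 adherence is 1 − 10/28 = 64.3%. Study drug compliance under the SAP rule is 100%. Tablets taken:

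| v | Parts D and E (o = 2) | Part F (o = 5) |
|---|---|---|
| 2 | 1 − 20/112 = 82.1% | 1 − 20/196 = 89.8% |
| 3 | 1 − 30/140 = 78.6% | 1 − 30/224 = 86.6% |
| 4 | 1 − 40/168 = 76.2% | 1 − 40/252 = 84.1% |

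Part D1 uses only 100 mg, so v = 1 is possible there, which gives 1 − 10/84 = 88.1%.

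**Missed VX-445 days needed to fall below 80% (D = 28)**

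- Any-drug compliance: 6 days (1 − 6/28 = 78.6%).
- Tablets, Parts D and E: 12, 10 and 9 days for v = 2, 3 and 4.
- Tablets, Part F: 20, 15 and 13 days for v = 2, 3 and 4.
- Study drug compliance under the SAP rule: never.

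**AE and disposition counts**

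One subject who stops only VX-445 in an arm of 18 (TC-high in Parts D2 and E, TC2-high in Part F) is 1/18 = 5.6 percentage points not shown. This gives the scale of one hypothetical case and does not predict how many will occur.

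**The case against.** A reader might infer more than the documents support, in four ways.

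1. *That such a subject counts as fully compliant.* This is true of one measure only. Percentage of tablets taken is reported beside it with the same 80% split, and it falls with every VX-445 tablet returned. At 3 or 4 VX-445 tablets a day, the 10-day example is already below 80% in Parts D and E.
2. *That the 80% deviation flag cannot see poor VX-445 adherence.* The rule is not tied to either measure. If it uses tablets, it fires after enough missed days. SAP 8.2.6 also lists incorrect doses as a potential deviation, does not claim its list is complete, and leaves classification to a blinded team.
3. *That stopping VX-445 alone for an AE is an expected course.* Protocol section 10 defines study drug as all components, 9.7.2 allows no dose modification for toxicity, and the liver rules in 9.8.2 act on study drug as a whole. The scheduled Day 29 stop is not an example either.
4. *That discontinuation due to AEs is the main tolerability result.* The stated primary safety endpoint is AE incidence. An AE that led to stopping VX-445 alone still enters the overall, severity and relationship tables (and the serious table if it applies) and the subject listing. The protocol records action taken for each AE.

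The SAP wording can also be defended as detail that the protocol left open, since the protocol does not say whether any or all drugs must stop.

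These arguments limit the point but do not remove it. The tablet count pools components and cannot show which was missed. An unplanned lapse is still possible with separate tablets. And the SAP restricts counts that the protocol left unrestricted, without listing the restriction in SAP 2.1.

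**Conclusion.** The point holds in a limited form. The all-drug condition makes study drug compliance, both AE-action tables and the premature-discontinuation count blind to a lapse in VX-445 alone. The tablet percentage registers the lapse only in diluted form: 64% VX-445 adherence appears as about 76% to 82% in Parts D and E and about 84% to 90% in Part F. Whether the 80% deviation rule catches such a subject depends on a choice that the SAP does not state.

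The tablet figures assume 2 to 4 VX-445 tablets a day, 28 days of dosing, and missed tablets being returned and counted. The 100% figure for study drug compliance does not depend on the tablet number.

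The consequence is confined to descriptive tables and the deviation listing. The primary efficacy analysis is unaffected: it uses subjects as randomised and keeps measurements after treatment discontinuation (SAP 7.2 and 8.3). This is a cheap improvement to reporting and not a threat to the trial's conclusions.

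**What to change.** - In SAP 8.2.1, 8.2.5 and 8.4.1, count interruption or discontinuation of any study drug. Add a separate row for VX-445 or its matching placebo, and keep the all-drug count as a sub-row.
- In SAP 8.2.5, report percentage of tablets taken by component.
- In SAP 8.2.6 and Appendix D, name the measure that triggers the 80% deviation.

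The cost is a change of definition and a few extra descriptive rows. Reported compliance may look slightly less favourable. Trial conduct and inference do not change.

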8.2.6 Important Protocol Deviations

An important protocol deviation (IPD) is a deviation that may significantly affect the completeness, accuracy, or reliability of the study data or that may significantly affect a subject's rights, safety, or well-being. IPD rules will be developed and finalized before database lock. The protocol deviations that should be considered as potential IPDs include, but are not limited to:

- Subject was enrolled in the study despite the violation of inclusion/exclusion criteria
- Subject was less than 80% compliant with study drug
- Subject received prohibited concomitant medications
- Subject received the wrong treatment or incorrect doses
- Subject remained in the study despite meeting withdrawal criteria

Occurrence of any of these events should be considered as potential IPDs, but a blinded team should categorize them as IPDs only if they have the potential to significantly affect the completeness, accuracy, or reliability of the study data or that may significantly affect a subject's rights, safety, or well-being.

IPDs will be provided in an individual subject data listing for each part. Details of the IPD rules are provided in [Appendix D](#).

8.3 Efficacy Analysis

All efficacy analyses described in this section will be based on the FAS, unless otherwise specified.

The analysis will include all available measurements through the last scheduled on-treatment visit including measurements after treatment discontinuation, per the visit windowing rules described in [Appendix B](#). Except the sensitivity analyses, the post-dose measurements on the same day (e.g. days when spirometry is repeated pre- and post-dose) will not be used for any model-based analyses, but only reported in descriptive safety analyses.

